#### 1.2.5.5. Immunogenicity Endpoints

Immunogenicity endpoints include serum anti-VIS649 ADA levels, the positive/negative results of a confirmatory ADA assay, antibody titer, and neutralizing antibody results, as applicable.

#### 1.2.5.6. Safety Endpoints

Safety evaluations performed during the study include physical examinations, measurement of vital signs, 12-lead electrocardiograms (ECGs), clinical laboratory evaluations including

hematology, serum chemistry, urinalysis, pregnancy, serum Ig levels, ADAs, monitoring of AEs and concomitant medications.

## 2. PARTICIPANT POPULATION

### 2.1. Population Definitions

The following participant populations will be evaluated and used for presentation and analysis of the data:

- **Intent-to-Treat (ITT) Population:** All participants who are randomized. Participants will be categorized by treatment they were randomized to receive.
- **Modified Intent-to-Treat (mITT) Population:** All randomized participants who received at least 1 dose of study treatment. Participants will be categorized by treatment that they were randomized to receive. The mITT population will be the primary population for assessment of efficacy.
- **Safety Population:** All randomized participants who received any amount of study treatment. Participants will be categorized by treatment received. Analysis of safety parameters will be performed using this population.
- **PK Population:** All randomized participants who received at least 1 dose of study treatment and have at least 1 post-dose evaluable serum concentration. The PK population will be the primary population for PK analyses.
- **Intensive PK Population:** All randomized participants who received at least 1 dose of study treatment, and consented to participation in the Intensive PK substudy (See Current Version of Protocol) and have at least 1 post-dose evaluable serum concentration.
- **PD Population:** All randomized participants who received at least 1 dose of study treatment and have baseline and at least 1 post-dose evaluable PD measure. The PD population will be the primary population for PD analyses.
- **Immunogenicity Population:** All randomized participants who are administered any amount of study treatment and have at least 1 pre-dose evaluable ADA measure.
- **Biomarker Population:** All randomized participants who consented to participate in the biomarker substudy (See Current Version of Protocol). Analysis of biomarker data will be performed on the Biomarker population (analyses performed with Biomarker Population data are not included in this SAP).
- **Per Protocol (PP) Population:** All randomized participants with  $\geq 75\%$  compliance and without any important protocol deviations involving inclusion/exclusion criteria, study treatment, or the primary efficacy analyses. Compliance (%) is calculated by  $100 \times (\text{number of doses received} / 12)$ . The primary efficacy analyses will be repeated for the PP population.

The PD and PK populations will be the population for the interim PK/Ig analyses (the interim PK/Ig analyses are not included in this SAP).

## **2.2. Protocol Deviations**

Important protocol deviations will be determined by a review of the data prior to unblinding of the study results. The Sponsor or designee will be responsible for producing the final determination (ie, major vs minor) in collaboration with Veristat, prior to final study database lock.

Protocol deviations will be collected and reported at the subject level, describing the context and/or reasons for the deviations such as re-screening, use of alternative endpoint ascertainment methods, and use of alternative or rescue treatments. Additional categories related to COVID-19 may be recorded and presented in the data listing.

Important protocol deviations will be presented in a data listing.

### **3. GENERAL STATISTICAL METHODS**

#### **3.1. Sample Size Justification**

The sample size for this study was calculated assuming a linear dose response (reduction of uPCR) of 0%, 15%, 30%, and 45% in placebo and VIS649 2, 4, and 8 mg/kg groups, respectively. Applying contrasts of -3, -1, 1, and 3 for the corresponding dose levels and analyzing uPCR on the natural log scale, the result is an expected mean change from baseline of 0, -0.163, -0.357, and -0.593 for placebo and VIS649 groups of 2, 4, and 8 mg/kg, respectively. Using an analysis of variance model with contrasts of -3, -1, 1, and 3 for the corresponding groups, a standard deviation (SD) of 0.87, 80% power, a 2-sided type I error rate of 0.05, and accounting for a dropout rate of ~ 20%, the required sample size is 36 participants per group, or 144 participants overall.

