### **3.7. Multiple Comparisons/Multiplicity**

Formal statistical hypothesis testing will be performed on the primary efficacy endpoint of linear dose response in change from baseline in uPCR on the natural log scale at Month 12, conducted at the 2-sided, 0.048 level of significance to preserve the study-wide 2-sided type I error rate at 0.05 while accounting for interim data review ([Section 4.8](#)). The inclusion of statistical tests for secondary endpoints is intended to yield supportive evidence related to the primary objective and will be descriptive in nature as no confirmatory conclusions are intended. Statistically significant results will be examined in sequence from high dose (8 mg/kg) to low dose (2 mg/kg) compared with placebo. Tests of probability are not planned for the exploratory endpoints so that multiplicity of statistical probability test results is not a consideration.

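### On SAP 3.1's own inputs, 36 per group less 20% dropout gives about 76–78% power for the linear contrast, not the stated 80%, mainly because of how dropout was allowed for

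*SAP*

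**What the plan says.** SAP 3.1 gives almost every input to its calculation. The effect is set by "assuming a linear dose response (reduction of uPCR) of 0%, 15%, 30%, and 45% in placebo and VIS649 2, 4, and 8 mg/kg groups", which it converts to an "expected mean change from baseline of 0, -0.163, -0.357, and -0.593 for placebo and VIS649 groups". The model and error rates are "Using an analysis of variance model with contrasts of -3, -1, 1, and 3 for the corresponding groups", with "a standard deviation (SD) of 0.87, 80% power, a 2-sided type I error rate of 0.05". The result is "accounting for a dropout rate of ~ 20%, the required sample size is 36 participants per group, or 144 participants overall". The section does not give the evaluable number per arm or say how dropout was applied.

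SAP 3.7 says that the linear dose-response test will be "conducted at the 2-sided, 0.048 level of significance", and SAP 4.3.1 and 4.8.1 repeat that level. SAP 3.9 says that participants who leave are not replaced. Protocol 9.2 has the same total of 144, the same power, reductions and dropout rate, and a study-wide alpha of 0.05, but an SD of 0.49 where the SAP has 0.87.

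**The concern.** A size that allows for 20% dropout should leave enough evaluable participants for 80% power once 20% have gone. Starting from 36, only 28.8 remain, which is fewer than the stated contrast, means and SD require. Two smaller mismatches sit in the same paragraph. The calculation uses alpha 0.05 while the test uses 0.048, and the log mean for a 45% reduction is printed as -0.593 although ln(0.55) = -0.598.

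What is at stake is how the result is read. The linear contrast is the only formally tested hypothesis in the trial. If it is not significant, readers will set that against a stated type II error of 20%, when SAP 3.1's own assumptions imply 22–24%. The estimate, its interval and the decision rule are not affected.

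**Working it through.** **Inputs (SAP 3.1 unless noted).** Contrast c = (-3, -1, 1, 3); printed means 0, -0.163, -0.357, -0.593; SD 0.87; alpha 0.05; dropout 20%; 36 per arm. Test alpha 0.048 (SAP 3.7, 4.3.1).

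**Contrast value.** L = sum of c x mean.
- Printed means: 0.163 - 0.357 - 3 x 0.593 = -1.973.
- Exact logs of 0.85, 0.70 and 0.55 (-0.1625, -0.3567, -0.5978): L = -1.988.

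**Power.** The sum of c² is 20. The noncentrality is |L| / (SD x sqrt(20/n)). Power comes from the noncentral t with 4n - 4 degrees of freedom, or from the normal approximation.

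**Reproducing the plan's figure.** With the normal approximation and z values 1.960 and 0.842, n = (1.960 + 0.842)² x 0.87² x 20 / L².
- Exact logs: n = 30.07 evaluable per arm.
- Printed means: n = 30.52.

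Multiplying by 1.2 gives 36.1 and 36.6 per arm, so 36 is recovered closely as 30 x 1.2. Dividing by 0.8 gives 37.6 and 38.2. The t-based requirements of 31 (exact logs) and 32 (printed means) give 31/0.8 = 38.75, so 39, and 32/0.8 = 40. None of the divisions by 0.8 gives 36.

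With the printed means and the t distribution, 31 evaluable gives 79.98%, just under the target. Strictly, 80% at alpha 0.05 needs 32 evaluable, or 40 enrolled, per arm.

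**Power at the planned size.** 36 x 0.8 = 28.8 evaluable per arm. For the printed means the noncentrality is 1.973 / (0.87 x sqrt(20/28.8)) = 2.721.

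| Convention, n = 28.8 | alpha 0.05 | alpha 0.048 |
|---|---|---|
| t, printed means | 77.0% | 76.4% |
| t, exact logs | 77.6% | 77.0% |
| normal, printed means | 77.7% | 77.2% |
| normal, exact logs | 78.3% | 77.8% |

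**Where the gap comes from (t, printed means).**
- 30 evaluable at alpha 0.05 gives 78.65%, already a little under 80% on a t basis.
- Having 28.8 and not 30 evaluable: 78.65% falls to 76.97%, about 1.7 points.
- Testing at 0.048: 76.97% falls to 76.42%, about 0.5 point.
- Replacing -0.593 by ln(0.55): 76.42% rises to 77.04%, about 0.6 point in the other direction.

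**Conditions under which 80% holds at alpha 0.048 with 36 enrolled.**
- Dropout: the t-based requirement is 31.4 evaluable (printed means) or about 31.0 (exact logs). The tolerable loss is 1 - 31.4/36 = 12.8% or 1 - 31.0/36 = about 14%.
- SD: with 28.8 evaluable, 80% needs an effective SD of about 0.83 (printed means) to 0.84 (exact logs).

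**Sensitivity to the SD.** With the protocol's 0.49, power at 28.8 per arm is above 99% and about 11 evaluable per arm would be enough.

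**The case against.** The strongest reply is that this is not the power of the planned analysis. SAP 4.3.1 fits an MMRM to Months 9 and 12 with baseline log uPCR and strata as covariates. A participant lost after Month 9 still contributes, and Protocol 7.1 encourages those who stop dosing to keep attending, so 20% dropout need not mean 20% missing information. A modest fall in residual variance would be enough: from 0.87 to 0.84 is 1 - (0.84/0.87)² = about 7%. This stands as a limit on the point. It does not rescue SAP 3.1, which rests its 80% on an ANOVA, claims no covariate gain and gives no correlation from which to compute one.

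Three further replies stand in part:
- The dropout rate is stated as approximate. A loss of one in six would leave 30 per arm and 78.1–79.4% power at 0.048, which is close to 80%.
- SAP 3.1 records a design calculation, and Protocol 9.2 also sizes at 0.05. Using 0.05 at the design stage is a small mismatch with the later test, not a serious error.
- A gap of two to four points changes nothing in conduct or analysis.

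A reader might infer that the trial is underpowered, that enrolment should rise to 40 per arm, or that the sponsor demonstrably multiplied by 1.2 in error. The documents do not support any of these. The first two ignore the MMRM and the unresolved SD. The third is an inference from a number that fits, because the SAP does not show the step. The power shortfall does not depend on it.

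**Conclusion.** The point holds, and it is minor. On SAP 3.1's contrast, SD of 0.87 and 20% dropout, no convention tried returns 80%: power is 77.0–78.3% at alpha 0.05 and 76.4–77.8% at 0.048. A single figure of 76% would overstate the gap, because it is the low end and uses the -0.593 that needs correcting. About 77% is the fair summary.

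The conclusion rests on a 20% loss of evaluable participants in each arm, on a simple ANOVA of those who remain, and on SD 0.87. The last condition matters most. SAP 3.1 and Protocol 9.2 give different SDs for the same sample size. If 0.87 is right, the shortfall stands and would be carried into any protocol text aligned with the SAP. If 0.49 is right, the shortfall disappears, but SAP 3.1 must then be rewritten anyway.

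**What to change.** First reconcile the SD between SAP 3.1 and Protocol 9.2. If 0.87 is kept, restate SAP 3.1 in one of two ways:

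1. 36 enrolled per arm, 28.8 evaluable after 20% dropout, fourth mean ln(0.55) = -0.598, two-sided alpha 0.048, about 77% power for the simple ANOVA contrast. Say that the MMRM may do better by an amount not quantified.
2. Keep 80% and state the assumption that delivers it at alpha 0.048: dropout of about 13–14%, or a covariate-adjusted SD of about 0.83–0.84 with its justification.

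In either case, state the evaluable number per arm and how dropout was applied. The cost is a wording change in the SAP and, under the first option, a slightly less favourable stated power. Enrolment, the model, the test and the decision rule stay as they are.

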#### **3.2. General Methods**

All collected data will be included in listings that will contain a relative study day if there is an evaluation date. Pretreatment and on-treatment study days are numbered relative to the day of the first dose of study medication which is designated as Day 1. The preceding day is Day -1, the day before that is Day -2, etc.

All output will be incorporated into Microsoft Word Rich Text Format files sorted and labeled according to the International Council on Harmonisation recommendations and formatted to the appropriate page size(s).

Tabulations will be produced for appropriate demographic, baseline, efficacy, PK, immunogenicity, safety, and exploratory parameters. For categorical variables, summary tabulations of the number and percentage of participants within each category (with a category for missing data) of the parameter will be presented. For continuous variables, the number of participants, mean, median, SD, standard error, minimum, and maximum values will be presented. For demographic continuous variables, the inter-quartile range (IQR) will also be presented.

All summary tables will be presented by treatment, including each individual VIS649 dose group, a pooled VIS649 dose group and placebo. For disposition, demographics and baseline characteristics summaries, an overall column will be included (ie, all participants).

Per study design, uPCR and eGFR measurements are collected up to Month 16. However, the treatment period is up to Month 12. Therefore, for the primary efficacy endpoint of 24-hour uPCR, the primary mixed model with repeated measures (MMRM) will include 24-hour uPCR at Months 9 and 12. For the secondary endpoint of 24-hour uPCR at 9 Months, the effect at Month 9 will be reported from the primary MMRM and included in the primary outputs. For the secondary endpoint of 24-hour uPCR at 16 Months, the same MMRM will be fitted but 24-hour uPCR at Months 9, 12 and 16 will be included (Section 4.3, 4.4).

### 3.3. Computing Environment

All descriptive statistical analyses will be performed using SAS statistical software Version 9.4 or higher, unless otherwise noted. Medical history and AEs will be coded using the Medical Dictionary for Regulatory Activities (MedDRA) (version 24.0 or newer). Concomitant medications will be coded using the World Health Organization (WHO) Drug Dictionary Enhanced (March 2022 or newer).

### 3.4. Baseline Definition and Change from Baseline

For all analyses, baseline will be defined as the most recent measurement prior to the first administration of study drug.

Change from baseline is calculated as the difference between a participant's treatment period value and baseline period value, where  $t_i$ =any post baseline time point and  $t_0$  is the baseline result:

$$\text{Change from baseline} = t_i - t_0$$

Percent of baseline is calculated as:

$$\text{Percent (\%)} \text{ of baseline} = 100 * t_1/t_0$$

The percent of baseline will be analyzed for IgA, IgG, IgM, IgA1, IgA2, and Gd-IgA1 endpoints.

The change from baseline on the natural log scale is calculated as:

$$\text{Change from baseline on the natural log scale} = \log(t_i) - \log(t_0) = \log\left(\frac{t_i}{t_0}\right)$$

The ratio change from baseline is calculated as:

$$\text{Ratio change from baseline} = \frac{t_i}{t_0}$$

Where  $t_i$ =any post baseline time point and  $t_0$  is the baseline result. The change from baseline on the natural log scale and the ratio change from baseline will be analyzed for the uPCR (both Schedule A and B Urine Collection) and 24-hour urine protein excretion.

### 3.5. Methods of Pooling Data

Data will be pooled across sites for each group. All VIS649 participants will be pooled across VIS649 doses in addition to a by-dose presentation.

### **3.6. Adjustments for Covariates**

Efficacy analyses will be adjusted for covariates including baseline measurements and strata.

### **3.7. Multiple Comparisons/Multiplicity**

Formal statistical hypothesis testing will be performed on the primary efficacy endpoint of linear dose response in change from baseline in uPCR on the natural log scale at Month 12, conducted at the 2-sided, 0.048 level of significance to preserve the study-wide 2-sided type I error rate at 0.05 while accounting for interim data review ([Section 4.8](#)). The inclusion of statistical tests for secondary endpoints is intended to yield supportive evidence related to the primary objective and will be descriptive in nature as no confirmatory conclusions are intended. Statistically significant results will be examined in sequence from high dose (8 mg/kg) to low dose (2 mg/kg) compared with placebo. Tests of probability are not planned for the exploratory endpoints so that multiplicity of statistical probability test results is not a consideration.

### **3.8. Subgroup and Sensitivity Analyses**

Subgroup analyses for primary efficacy endpoint will be performed as described in [Section 4.3.2](#).

Sensitivity analyses will be performed as described in [Section 4.3.3](#) for primary efficacy endpoint and in [Section 4.4.2](#) for selected secondary efficacy endpoints.

### **3.9. Withdrawals, Dropouts, Loss to Follow-up**

Participants who withdrew from the study, were discontinued, or lost to follow-up will not be replaced.

### **3.10. Missing Data**

In general, there will be no imputation performed for missing data, including efficacy, safety, PK, PD, and ADA, unless otherwise specified. All data recorded on the case report form will be included in data listings that will accompany the CSR.

Missing data due to discontinuation of treatment, withdrawal from the trial or missed endpoint ascertainment will be reported at the subject level with a description of the context and/or reason for the missing data (eg, 'COVID-19').

For the primary efficacy endpoint, if a result is missing or not evaluable for 24-hour uPCR, and there is an unscheduled visit within 30 calendar days of the nominal visit date, the unscheduled visit assessment will be treated as the nominal timepoint.

For the analysis of AE, only partial dates will be imputed unless otherwise specified. The algorithms for imputation of partial dates depend upon the parameter, as follows:

- If the day of the month is missing, the onset day will be set to the first day of the month unless it is the same month and year as study treatment. In this case, in order to conservatively report the event as treatment-emergent, the onset date will be assumed to be the date of treatment.
- If the onset day and month are both missing, the day and month will be assumed to be January 1, unless the event occurred in the same year as the study treatment. In this case, the event onset will be coded to the day of treatment to conservatively report the event as treatment-emergent.
- A missing onset date will be coded as the day of treatment.

Adverse events with missing relation will be considered related. Adverse events with missing severity will be considered severe.

For the analysis of concomitant medication, incomplete start/stop dates will be imputed based on the following imputation rules:

- If start date is completely missing, start date will not be imputed.
- If start year is present and month and day are missing, or year and day are present and month is missing, set start month and day to January 1.
- If start year and month are present and day is missing, set start day to 1st day of the month.
- If end date is completely missing, end date will not be imputed.
- If end year is present and month and day are missing, or year and day are present and month is missing, set end month and day to December 31.
- If end year and month are present and day is missing, set end day to last day of the month.
- The imputed dates must be logical, ensuring that no end date is after database lock or death or before the start date.

### **3.11. Visit Windows**

If a participant is unable to attend a visit within 7 days of the scheduled infusion, they may still receive an infusion within the next 7 days; this will be recorded as a protocol deviation and will still be recorded for that visit. However, if there is any further delay, that dose will be skipped, and the participant will receive subsequent doses as per the schedule. The participant will not receive additional doses to make up for the missed dose(s). In data listings, all available data and the relative day of all dates will be presented.

Visits will be included in the analyses as labelled on the case report form with the exception of the following Visit/Month labels:

- M12/ET; where ET = Early Termination
- W16/EOS; where EOS = End of Study

If the 'M12/ET' visit does not occur within Days 346 - 375, relative to the first dose date, then the relative day for the visit will be determined using [Table 5](#) and the visit label will be updated with the Month (M) of the relative day of the visit. Eg, 'ETM3' will be the visit label if the relative day of the 'M12/ET' visit was within days 76 – 105.

If the 'W16/EOS' visit does not occur within Days 454 – 492, relative to the first dose date, then the relative day for the visit will be determined using [Table 5](#) and the visit label will be updated with the Month (M) of that relative day. Eg, 'EOSM6' will be the visit label if the relative day of the 'W16/EOS' visit was within days 166 - 195.

**Table 5 Visit Windows**

Visit/Month	Relative Day
Screening	-30 to -1
Baseline	1 (first dose date) a
M0	2 to 12
M0	13 to 24
M1	25 to 45
M2	46 to 75
M3	76 to 105
M4	106 to 135
M5	136 to 165
M6	166 to 195
M7	196 to 225
M8	226 to 255
M9	256 to 285
M10	286 to 315
M11	316 to 345
M12	346 to 375
M13	376 to 405

M14	406 to 453
M16	454 to 492

a If patient has no first dose date, Day 1 will be the randomization date.

## **4. STUDY ANALYSES**

### **4.1. Participant Disposition**

A tabulation of the disposition of participants will be presented by group. Summaries will include the number of participants screened, failed screening, enrolled, randomized and treated, participants in each stratification factor (Japan and ROW), number of participants in each study population and number of participants who discontinued as well as the reasons for discontinuation.

A by-group, by-participant data listing of study completion information including the reason for premature study withdrawal, if applicable, will be presented. A data listing will also be presented for the inclusion/exclusion criteria not met/met, visits completed, and whether any visit was related to COVID-19.

### **4.2. Demographics and Baseline Characteristics**

Demographics and baseline characteristics, including medical history, will be summarized and presented by group and overall, using the ITT population. Age, height, weight, body mass index (BMI) and baseline ECG findings will be summarized using descriptive statistics (number of participants, mean, SD, median, minimum, and maximum). The number and percentage of participants in each sex, ethnicity, race and baseline ECG interpretation category will be presented.

Baseline medical history tabulation will include whether the participant experienced any significant illnesses, pre-existing conditions or surgeries, prior tonsillectomy and prior hypertension defined by the following Preferred Term: ‘Hypertension’.

Baseline kidney biopsy history tabulation will include time since biopsy, method used for biopsy interpretation, mesangial hypercellularity, endocapillary proliferation, segmental glomerulosclerosis tubular, tubular atrophy/interstitial fibrosis, crescents and immunofluorescence intensity for IgA, IgG, IgM, C3, C4 and C1q.

Baseline ACEi/ARB history tabulation will include ACEi/ARB medication(s) information from the last 3 months at a minimum or previous 12 months (if known).

Baseline Systemic Immunosuppressive Agent (SIA) history tabulation will include details of any previous SIA medication use.

All demographic, baseline characteristics, medical history, kidney biopsy history, ACEi/ARB history, 12-lead ECG, serology, pregnancy, Hemoglobin A1c, and blood sample for deoxyribonucleic acid (DNA) results will be provided in data listings.

